## 5.5. SUBCOHORT PER-PROTOCOL SET

### 5.5.1. SUBCOHORT PER-PROTOCOL SET FOR ANALYSIS OF IMMUNOGENICITY AT DAY 521

The analysis set will contain all subjects included in the Per-protocol Set, who received the Dose 3 on an active arm, with no protocol deviations leading to exclusion until Day 521 and with at least 1 immunogenicity data available at Day 521.

### 5.5.2. SUBCOHORT PER-PROTOCOL SET FOR ANALYSIS OF IMMUNOGENICITY AT DAY 670

The analysis set will contain all subjects included in the Per-protocol Set, who received the Dose 3 on an active arm, with no protocol deviations leading to exclusion until Day 670 and with at least 1 immunogenicity data available at Day 670.

Document:	\\\usadc-nas01a\cp_ops\PROJECTS\Glaxo SmithKline\GSK208109_BZA47109\SAP		
Author:	PPD	Version Number:	3.0
		Version Date:	27SEP2021

## 5.6. COVID-19 SET

The analysis set will contain all subjects included in the exposed set who were not able to go to the site for the Visit 5 (Day 61) on schedule, due to study being paused during COVID-19, and as a result, had their immunogenicity samples collected outside of the protocol specified interval. This analysis set will be used for additional descriptive summaries of immunogenicity variables.

Analysis	Enrolled Set	Exposed Set	Un-solicited Safety Set*	Solicited Safety Set	Full Analysis Set**	Per-protocol (PP) Set		Subcohort PP Set		COVID-19 Set
						PP Set Day 61	PP Set Day 180	PP Set Day 390	PP Set Day 521	
Subject Disposition	✓									
Baseline Assessments		✓	✓			✓	✓	✓	✓	✓
Concomitant Medications		✓								
Exposure		✓								
Immunogenicity Analysis					✓	✓	✓	✓	✓	✓
Protocol Deviations		✓								
Adverse Events			✓	✓						
Other Safety (lab, vitals)		✓								

\* The safety/reactogenicity analysis will be first performed on the exposed set. If  $\geq 10\%$  of subjects have missing information for unsolicited symptoms, then the analyses on the unsolicited safety set will be performed.

\*\* Analysis in this set will be performed if the percentage of vaccinated subjects with serological results excluded from the Per-protocol Set for analysis of immunogenicity is 10% or more

## 6. GENERAL CONSIDERATIONS

The safety summaries, data listings and figures as well as the statistical analysis of the variables will be the responsibility of the study biostatistician at IQVIA.

---

Document:	\\usadc-nas01a\cp_ops\PROJECTS\Glaxo SmithKline\GSK208109_BZA47109\SAP
Author:	PPD
	Version Number: 3.0
	Version Date: 27SEP2021

Template No: CS\_TP\_BS016 – Revision 5  
 Effective Date: 01Apr2018

Reference: CS\_WI\_BS005

## 6.1. SUMMARY STATISTICS

For qualitative variables, the population size (N for sample size and n for available data) and the percentage (of available data) for each class of the variable will be presented. Quantitative variables will be summarized using descriptive statistics, including N (with data available), Nmiss (with missing data), mean, standard deviation (SD), coefficient of variation (CV%), median, Q1, Q3, minimum, and/or maximum values. Geometric mean will be included for immunogenicity parameters, where applicable. Coefficient of variation will not be presented for change from baseline results.

The exact two-sided 95% CIs for a proportion within a group will be calculated using the Clopper-Pearson exact method.

The geometric mean antibody titers (GMTs) calculations will be performed by taking the anti-log of the mean of the log10 titer transformations. Confidence interval for geometric means will be derived by raising 10 to the confidence interval associated with mean of log10 values i.e. CI of geometric mean =  $10^{(CI \text{ for the mean of log10 values})}$ . All subjects with data will be considered. Subjects whose antibody titers are below the cut-off of the assay will be given an arbitrary value of half the cut-off for the purpose of GMT calculation.

## 6.2. TREATMENT SUMMARIZATION

In general, data will be presented for each treatment group:

Age	Treatment
50-70 Y	CDIFF Ag + AS01 B
	CDIFF Ag
	Placebo
18-45 Y	CDIFF Ag
	Placebo

Data for all study subjects combined will also be presented when appropriate. Analysis by age in older adult cohort will be performed by age strata (50-59 years old and 60-70 years old) for the descriptive immunogenicity analyses if at least 6 subjects are available in these subgroups and in at least one active arm.

## 6.3. PRECISION

Safety data (vital signs, laboratory parameters) and immunogenicity data will be reported to the same

Document:	\\usadc-nas01a\cp_ops\PROJECTS\Glaxo SmithKline\GSK208109_BZA47109\SAP	
Author:	PPD	Version Number: 3.0 Version Date: 27SEP2021

Template No: CS\_TP\_BS016 – Revision 5  
Effective Date: 01Apr2018

Reference: CS\_WI\_BS005

precision as the source data.

For the reporting of descriptive statistics, the mean, median, Q1, Q3, standard deviation, standard error and confidence intervals will be presented to one digit more precision than the source data. The minimum and maximum will be presented to the same precision as the source data. Coefficient of variation (%) will always be reported to 1 decimal place. P-values, if any, shall be reported to four decimal places or as <0.0001.

The number of decimals used when displaying geometric mean titers (GMT) and their confidence limits is shown in the following table:

GMT value	Number of decimals to display
<0.1	3
>=0.1 and <10	2
>=10 and <1000	1
>=1000	0

When multiple categories of GMT/GMC values are present in the same table, the number of decimals displayed should match that of the smallest category (i.e. the one with the higher number of decimals). GMFR or GMT/GMC ratios and their confidence limits will be displayed with 2 decimals regardless of the actual values.

## 6.4. REFERENCE START DATE AND STUDY DAY

Study Day will be calculated from the reference start date and will be used to show start/stop day of assessments and events.

Reference start date is defined as the day of the first dose of study vaccination, (Day 1 is the day of the first dose of study treatment) and will appear in every listing where an assessment date or event date appears.

- If the date of the event is on or after the reference date, then:

Study Day = (date of event – reference date) + 1.

- If the date of the event is prior to the reference date, then:

Study Day = (date of event – reference date).

In the situation where the event date is partial or missing, Study Day, and any corresponding durations will appear partial or missing in the listings. Refer to Section 7.1.1 for rules applicable on partially completed dates when used in calculations.

---

Document:

\\usadc-nas01a\cp\_ops\PROJECTS\Glaxo SmithKline\GSK208109\_BZA47109\SAP

Author:

PPD

Version Number:

3.0

Version Date:

27SEP2021

Template No: CS\_TP\_BS016 – Revision 5

Reference: CS\_WI\_BS005

Effective Date: 01Apr2018

#### 6.4.1. ATTRIBUTING EVENTS TO VACCINE DOSES

The dose relative to an event is the most recent study dose given to a subject prior to the start of a given event. For example, if the start date of an adverse event is between Dose 1 and Dose 2, the relative dose will be Dose 1.

If an event starts on the same day as a study dose, the relative dose will be derived from the additional information provided in the CRF using the contents of the flag indicating if the event occurred before or after vaccination. If 'after vaccination' is selected, the relative dose for the event will be the one administered on the start day of the event. If 'before vaccination' is selected, the relative dose for the event will be the dose prior to this one. Where applicable, the event will be classified as "pre-treatment".

### 6.5. BASELINE

Baseline is defined as the last scheduled non-missing measurement taken prior to dosing and will correspond to Day 1, predose for immunogenicity assessments, hematology and biochemistry, and vital signs. However, if a subject is missing the planned baseline result, the previous non-missing evaluation will become the baseline value.

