
 To evaluate the humoral immunogenicity induced by IM doses of the C. difficile F2 fusion protein when administered with or without AS01_B adjuvant according to a 0, 1-month schedule, in healthy adults aged between 18-45 years and between 50-70 years followed by an additional dose administered approximately 15 months after Dose 2 in a subcohort of subjects aged 50-70 years, up to study end. 	
 Humoral response to the investigational C. difficile F2 fusion protein when administered with or without AS01_B adjuvant, at Days 1, 31, 61, 180, 390, 491, 521 and 670. 
 Serum neutralizing antibody titers anti-Toxin A and anti-Toxin B, as measured by TNA. Serum antibody concentration anti-Toxin A and anti-Toxin B, as measured by ELISA.

AE = adverse event; AS01_B = an adjuvant system containing MPL, QS-21 and liposome (50 µg MPL and 50 µg QS-21); *C. difficile* = *Clostridium difficile*; ELISA = enzyme-linked immunosorbent assay; FDA = Food and Drug Administration; GSK = GlaxoSmithKline Biologicals SA; IM = intramuscular; MedDRA = Medical Dictionary for Regulatory Activities; MPL = 3-O-desacyl-4'-monophosphoryl lipid A; pIMD = potential immune-mediated disease; QS-21 = *Quillaja saponaria* Molina, fraction 21 (Licensed by GSK from Antigenics Inc., a wholly owned subsidiary of Agenus Inc., a Delaware, USA corporation); SAE = serious adverse event; TNA = toxin neutralization assay.

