4.2.2 Rationale for Randomization and the Use of Placebo

Randomized, placebo-controlled studies are widely considered to be the most rigorous method for the efficacy evaluation of treatments or prevention interventions. To be ethical, clinical

research requires balancing rigorous science with the protection of subjects. The use of placebo controls in studies for conditions with no effective treatment is widely accepted.⁶ Up to date, there is no established standard of care to prevent CDI.

Likewise, the Declaration of Helsinki allows placebo controls and states: “Where for compelling and scientifically sound methodological reasons the use of placebo is necessary to determine the efficacy or safety of an intervention and the patients who receive placebo will not be subjected to additional risks of serious or irreversible harm.”⁷

Randomization is used to reduce bias of selection and the placebo group is included as a control for the reactogenicity, the safety and the immunogenicity assessments.

The third dose of the vaccine is being given to the subjects recruited in the active groups of the last step of the study, to demonstrate if a similar kinetics in terms of anti-Toxin A/Toxin B can be achieved with the F2 antigen formulation with or without an adjuvant. Therefore, the third dose will not be given to the subjects receiving placebo.

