### 6.6. COMMON CALCULATIONS

For quantitative safety measurements (e.g. vital signs, laboratory parameters), change from baseline will be calculated as:

- Test Value (after baseline) – Baseline Value

For immunogenicity measurements, change from baseline will be calculated as:

- Test Value (after baseline)/Baseline Value

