## 15. IMMUNOGENICITY ANALYSIS

The primary analysis will be based on the Per-protocol Set for analysis of immunogenicity. If, in any study group, the percentage of vaccinated subjects with serological results excluded from the Per-protocol Set for analysis of immunogenicity is 10% or more, a second analysis based on the Full Analysis Set will be performed.

The analysis of subjects receiving Dose 3 on an active arm will be based on the Subcohort Per-protocol Set for analysis of immunogenicity.

Numerical serology results will be derived from the content of IS.ISORRES in the SDTM dataset. For

Document:	\usadc-nas01a\cp_ops\PROJECTS\Glaxo SmithKline\GSK208109_BZA47109\SAP		
Author:	PPD	Version Number:	3.0
		Version Date:	27SEP2021

Template No: CS\_TP\_BS016 – Revision 5  
Effective Date: 01Apr2018

Reference: CS\_WI\_BS005

assays with a specific cut-off, the following derivation rules apply:

IS.ISORRES	Derived value
“< value” and value is <= assay cut-off	cut-off/2
“< value” and value is > assay cut-off	value
“> value” and value is < assay cut-off	cut-off/2
“> value” and value is >= assay cut-off	value
“value” and value is < cut-off	cut-off/2
“value” and value is >= cut-off	value
All other cases	missing

The following immunogenicity variables will be assessed:

- Anti-Toxin A neutralizing antibody titers (using HT29 cell line)
- Anti-Toxin B neutralizing antibody titers (using HCT116 cell line)

A listing of collection dates and times for the immunogenicity variables will be presented for subjects within each treatment group. For each test method, the neutralizing antibody titers from TNA assay will be listed and summarized by treatment groups across all scheduled timepoints during entire study.

For each study group, each age group (18-45 Y versus 50-70 Y) and/or subcohort (as applicable), at each timepoint that blood samples are collected for humoral immune response and for each assay:

- Percentage of subjects above the assay cutoff with their exact 95% CI will be tabulated
- Geometric mean titers and their 95% CI will be calculated
- Geometric mean fold-rise with their exact 95% CI will be tabulated
- Percentage of subjects with >=2, 4, 8, 16, 32, 64 fold-rise from baseline for each assay
- Percentage of subjects with >=2, 4, 8, 16, 32, 64 fold-rise from baseline for both anti-Tox A and anti-Tox B for neutralizing titers
- Antibody titers will be investigated using Reverse Cumulative Curves

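### The visible SAP defines every fold-rise against Day 1, so the planned tables give neither a confidence interval for the Dose 3 boost nor the proportion of subjects who responded to Dose 3

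*SAP*

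**What the plan says.** SAP 6.5 fixes one immunogenicity baseline: "Baseline is defined as the last scheduled non-missing measurement taken prior to dosing and will correspond to Day 1, predose for immunogenicity assessments". The words on dosing might suggest that the last sample before each dose could serve, but the same sentence ties the value to Day 1. SAP 6.6 defines immunogenicity change as the later value divided by that baseline.

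SAP 15 lists the tables. Among them are "Geometric mean fold-rise with their exact 95% CI will be tabulated", "Geometric mean titers and their 95% CI will be calculated" and "Percentage of subjects with >=2, 4, 8, 16, 32, 64 fold-rise from baseline for each assay". They are due "For each study group, each age group (18-45 Y versus 50-70 Y) and/or subcohort (as applicable), at each timepoint that blood samples are collected". Protocol 3.0 lists the humoral sampling "at Days 1, 31, 61, 180, 390, 491, 521 and 670", and Protocol 1.3 (Table 6, note e) has the Day 491 blood drawn before Dose 3.

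Protocol 4.2.2 gives the purpose of the third dose: "to demonstrate if a similar kinetics in terms of anti-Toxin A/Toxin B can be achieved". The Amendment 03 rationale adds that anti-Toxin B neutralizing responses after Dose 2 were lower in subjects without quantifiable antibodies at baseline, so that a third dose might be needed. SAP 15 bases the analysis of Dose 3 recipients on the Subcohort Per-protocol Set. It also plans a mixed model for the difference between treatments in those subjects. The text after that model, and the whole of SAP 15.1, is redacted.

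**The concern.** The question for Dose 3 is an increment: how far titers rise from just before the dose, and whether they end higher than after two doses. Placebo subjects do not receive Dose 3, and subjects receiving two doses conclude at Day 390 (Protocol 4.2.2 and 4.4). There is therefore no concurrent control at Day 521, and within-subject change carries the evidence. The visible Dose 3 model compares treatments, that is, adjuvanted with unadjuvanted vaccine. It is not described as estimating the change from before to after the dose.

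A fold-rise from Day 1 at Day 521 combines what remains of Doses 1 and 2 with the effect of Dose 3. For subjects below the assay cut-off on Day 1, the subgroup that motivated the dose, the denominator is also half the cut-off by convention (SAP 6.1). At stake are the precision of the boost and the count of boost responders.

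**Working it through.** **Inputs.** The SD of the log10 fold-rise is 0.84 (Toxin A) and 1.4 (Toxin B), with 36 evaluable per arm (Protocol 9.2). The Step 4 active arms have about 25 and 35 subjects (Protocol 4.1). Carrying over the 20% loss assumed in Protocol 9.2 leaves 20 and 28, or 48 in all. Table 21 lists about 50 at Visits 10 and 11.

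**1. The plan's own figure.** CI = GMFR × 10^(± t(0.975, n−1) × SD/√n). For GMFR 10 and n = 36:
- Toxin A: 2.030 × 0.84/6 = 0.284, giving [5.20; 19.24]. Table 23 has [5.20; 19.23].
- Toxin B: 2.030 × 1.4/6 = 0.474, giving [3.36; 29.76]. Table 23 has [3.36; 29.79].

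Table 23 is reproduced. It covers one rise from before to after vaccination and says nothing about Dose 3.

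**2. What the Day 1 tables do give.** In the same subjects, the Day 1 value cancels:

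GMFR(521/491) = GMFR(521/1) ÷ GMFR(491/1).

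With assumed Day 1-based GMFRs of 8 at Day 491 and 32 at Day 521, the boost is 32/8 = 4.0, whatever the correlation.

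**3. What they do not give: the CI.** The SD of the paired log10 difference is SD × √(2(1−ρ)), where ρ is the correlation between the two log10 fold-rises. The same SD is assumed on both days. Then CI = 4 × 10^(± t × SD × √(2(1−ρ))/√n).

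| SD | n | ρ = 0 | ρ = 0.5 | ρ = 0.9 |
|---|---|---|---|---|
| 1.4 | 28 | [0.68; 23.4] | [1.15; 14.0] | [2.29; 7.00] |
| 1.4 | 20 | [0.47; 33.8] | [0.88; 18.1] | [2.04; 7.85] |
| 0.84 | 28 | [1.38; 11.6] | [1.89; 8.47] | [2.86; 5.59] |
| 0.84 | 20 | [1.11; 14.4] | [1.62; 9.89] | [2.67; 6.00] |

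The listed tables would look the same across a row, because they do not report ρ. At SD 1.4, whether the interval excludes 1 depends on ρ.

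**4. Responder rate with no Dose 3 effect.** With log-normal fold-rises and a Day 491 GMFR of m that Dose 3 leaves unchanged, the share at or above 4-fold from Day 1 at Day 521 is 1 − Φ((log10 4 − log10 m)/SD).

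| SD | m = 2 | m = 4 | m = 8 |
|---|---|---|---|
| 0.84 | 36% | 50% | 64% |
| 1.4 | 41.5% | 50% | 58.5% |

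**5. Why comparing the two rows does not give boost responders.** As a constructed example, take two subjects with the same Day 1 titer. Their fold-rises from Day 1 are 2 and 8 at Day 491, and 8 and 32 at Day 521.
- If 2 becomes 8 and 8 becomes 32, both rose 4-fold after Dose 3, so 100% are boost responders at 4-fold.
- If 2 becomes 32 and 8 stays at 8, one rose 16-fold and one did not rise, so 50% are.

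In both cases the Day 491 GMFR is √(2×8) = 4, the Day 521 GMFR is √(8×32) = 16, and every threshold percentage and GMT is the same. The tables show the net shift but not who moved.

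**6. Same subjects.** The Subcohort Per-protocol Sets require a result at Day 521 or Day 670, not at Day 491 (SAP 5.5). Table 21 lists about 60 samples at Visit 8. The division in step 2 is exact only if the same subjects stand in both rows.

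**The case against.** The strongest reply is that by-timepoint tables already show the boost. Take a subject with titers 10, 160, 80 and 160 at Days 1, 61, 491 and 521. The Day 1-based rows read 16, 8 and 16. Anyone reading them in sequence sees a 2-fold rise after Dose 3 (16/8) and no gain over two doses (16/16). An absent effect looks present only if the Day 521 row is read alone. This stands. A reader might infer that the planned tables cannot separate Dose 3 from Doses 1 and 2, but the documents do not support that, because Day 491 is a tabulated timepoint.

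A reader might also argue that the Day 61 and Day 521 GMTs must come from different populations. SAP 15 allows tabulation by subcohort at each sampling timepoint, so Day 61 values in Dose 3 recipients are within the plan as written. What remains is the narrower point that the sets do not require a Day 491 result.

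Third, the text after the Dose 3 model and in SAP 15.1 is redacted and could contain an analysis based on Day 491. The statement must therefore be limited to the visible SAP.

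Finally, the study tests no hypotheses (Protocol 9.1), the secondary endpoint is the titers themselves, the tables by Day 1 serostatus are already planned, and individual titers will be listed, so the ratios could be computed later. That limits the weight of the point. It does not supply the missing CI or responder rate, which are better specified in advance than derived afterwards.

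**Conclusion.** The point holds for the visible text. No Day 491 baseline is defined, and no paired Day 521/Day 491 fold-rise with its 95% CI or Dose 3 responder rate is listed. The boost point estimate can be recovered by division in a common set of subjects.

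The missing CI matters in size. For a 4-fold boost with n = 28 and SD 1.4, the lower limit is 0.68 at ρ = 0 and 2.29 at ρ = 0.9. A 4-fold responder rate from Day 1 of 36% to 64% at Day 521 is compatible with no Dose 3 effect. These figures assume the SDs of Protocol 9.2 at both days, 20% loss, log-normal fold-rises, and the illustrative boost and Day 491 GMFRs. The documents give no ρ.

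A claim that all fold-rises in the plan are tied to Day 1 would go too far, because redacted sections cannot be checked. No alpha, power or sample size depends on this. It is a low-cost improvement to a descriptive analysis.

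**What to change.** Keep the Day 1-based tables. In SAP 6.5, define Day 491 predose as a second baseline for Dose 3 recipients. In SAP 15, for recipients with both samples of the pair, add:
- within-subject GMFR with 95% CI for Day 521/Day 491 (boost) and Day 521/Day 61 (gain over two doses), with the number of pairs shown;
- the percentages with at least 2-, 4-, 8-, 16-, 32- and 64-fold rise from Day 491;
- both of these overall and by Day 1 serostatus, where the SAP's minimum of 6 subjects is met.

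A Day 670/Day 180 ratio may look like a natural measure of persistence. It would compare 179 days after Dose 3 with 149 days after Dose 2, in windows (170 to 190 and 140 to 160 days) that do not overlap. Leave it out, or show it only with that caveat.

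The cost is a few table rows. No new samples or visits are needed. If the redacted text already contains these ratios, a cross-reference from SAP 6.5 is enough.

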### 6.6. COMMON CALCULATIONS

For quantitative safety measurements (e.g. vital signs, laboratory parameters), change from baseline will be calculated as:

- Test Value (after baseline) – Baseline Value

For immunogenicity measurements, change from baseline will be calculated as:

- Test Value (after baseline)/Baseline Value

### 6.7. SOFTWARE VERSIONS

All derivations, statistical analyses, summaries, graphs and listings will be generated using SAS version 9.4 or higher (SAS Institute, Inc., Cary, North Carolina).

---

Document:	\\\usadc-nas01a\cp_ops\PROJECTS\Glaxo SmithKline\GSK208109_BZA47109\SAP		
Author:	PPD	Version Number:	3.0

Template No: CS\_TP\_BS016 – Revision 5  
Effective Date: 01Apr2018

Reference: CS\_WI\_BS005

## 7. STATISTICAL CONSIDERATIONS

### 7.1. MISSING DATA

Missing immunogenicity data will be handled as described in Section 15. Following imputation will be used for statistical calculations (and not for subject listings):

#### 7.1.1. DATES

When partially completed birth dates (i.e. with missing day or month) are used in calculations, the following standard rules will be applied:

- A missing day will be replaced by 15
- A missing day and month will be replaced by June 30th

The following exceptions apply:

- Adverse event start dates with missing day:
  - o If the event starts in the same month as at least one of the study doses, the contents of AE.AESTRTPT (the flag indicating if the event occurred before or after vaccination) will be used to complete the date. If 'after vaccination' is selected, the imputed start date will match the first (or only) study dose given during that month. If 'before vaccination' is selected, the imputed date will be one day before the first (or only) study dose given during that month.
- Adverse event start dates with missing day and month:
  - o If the event starts in the same year as at least one of the study doses, the contents of AE.AESTRTPT (the flag indicating if the event occurred before or after vaccination) will be used to complete the date. If 'after vaccination' is selected, the imputed start date will match the first (or only) study dose given during that year. If 'before vaccination' is selected, the imputed date will be one day before the first (or only) study dose given during that year.

All other cases of incomplete AE or concomitant medication/vaccination start date will follow the standard rules as outlined in Section 6.4.

